7.4. To estimate the proportion of acquired rifampicin resistance among failures and relapses

Proportions per treatment arm will be estimated together with 95% Wilson confidence intervals, using the number of failure / relapse cases without mutation detected at diagnosis as the denominator.

7.5. To compare the predictive value of auramine with FDA staining at 2 weeks to predict unfavourable outcomes

The ROC curves of auramine resp. FDA staining at 2 weeks to predict adverse treatment outcome will be plotted and compared using the nonparametric approach of DeLong, DeLong, and Clarke-Pearson (1988). In addition, the proportion of referrals to rapid DST will be compared between auramine and FDA using the chi-squared or Fisher exact test.

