An interim analysis is thus planned at the time the last recruited patient finishes treatment, i.e. about 9 months after the end of recruitment. It will focus on assessment of drug toxicity versus suggested benefits of the intervention. This analysis will be primarily performed for the go/no-go decision and design considerations for the cluster-randomized trial. The decision on proceeding to the cluster randomized study will be based on the absence of excess toxicity, a trend toward a reduction of unfavourable outcomes (excluding relapse), and possible favourable effects on initially present low-resistance mutations / mutations acquired during treatment. It will also allow to adapt the design of the larger study particularly regarding the algorithm for resistance screening, and whether or not treatment shortening could be justified with rapid initial conversion.

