3.1 Primary endpoints

The primary efficacy endpoint is the incidence of adverse treatment outcomes. Following the WHO guidelines from 2010¹⁸, as currently in use in the NTP in Bangladesh, outcomes are defined as follows:

- Cured: A patient whose smear or culture was positive at the beginning of treatment but who was smear- or culture-negative in the last month of treatment and on at least one previous occasion.
- Completed: A patient who completed treatment but who does not have a negative sputum smear or culture result in the last month of treatment and on at least one previous occasion.

- Relapse: Cured previously from TB or completed treatment for TB and now having bacteriologically positive sputum for TB (at 12 months follow-up or at an earlier time point)
- Default: The patient whose treatment was interrupted for ≥ 2 consecutive months or more.
- Failure: Sputum positive for TB at 5 months or later during treatment. In line with current WHO recommendations, patients detected with MDR-TB or rifampicin resistance before this or another outcome applies and switched to the MDR-TB regimen will be excluded from the outcome analysis.¹⁸ Failure will also be declared if the regimen has to be changed for at least 2 drugs due to adverse events.
- Death: All-cause mortality between case registration and end of TB treatment (related or not to TB or TB treatment)
- Transfer out: A TB patient who transferred out to another recording and reporting unit and whose treatment outcome is unknown.

Analyses will be performed using the NTP smear-based recurrence (failure, relapse) definitions, but as a secondary approach culture-based definitions will be used.

Safety:

The primary safety endpoint will be the occurrence of any of the following:

- Serious Adverse Events
- Grade 3-4 Liver Toxicity following NIH common toxicity criteria (CTC), including transaminase increases to $>5-20$ ULN (grade 3), or > 20 ULN (grade 4)

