 - refer for rapid DST if indicated by algorithm; switch to MDR if rifampicin resistant
 - otherwise continue high-dose treatment
 - o **Control arm only:**

- refer for rapid DST if still fever (temperature $\geq 38^{\circ}\text{C}$); switch to MDR if rifampicin resistant
 - Enquire, register adverse effects. Stop all drugs and refer in case of hepatitis suspicion (feeling sick, anorexia, vomiting, jaundice)
- Visit after four weeks V3: intervention + control arm
 - Clinical check, weight, temperature: improved signs and symptoms of TB?
 - Give treatment, record attendance
 - Liver test
 - Enquire, register adverse effects. Stop all drugs and refer in case of hepatitis suspicion (feeling sick, anorexia, vomiting, jaundice)
- Visit after 2 months V4: intervention + control arm
 - Clinical check, weight, temperature: signs and symptoms of TB absent?
 - Give treatment, record attendance
 - Cat. 1: sputum smear for AFB
 - Refer for rapid DST if AFB-positive (auramine and FDA) and clinically poor evolution; switch to MDR treatment if rifampicin resistant
 - Liver test
 - Enquire, register adverse effects. Stop all drugs and refer in case of hepatitis suspicion (feeling sick, anorexia, vomiting, jaundice)
- Visit after 3 months V5: intervention + control arm
 - Clinical check, weight, temperature: signs and symptoms of TB absent?
 - Give treatment, record attendance
 - Sputum smear for AFB: all Cat. 2 and Cat. 1 patients positive at month 2
 - Refer for rapid DST if AFB-positive (auramine and FDA); switch to MDR treatment if rifampicin resistant
 - Enquire, register adverse effects. Stop all drugs and refer in case of hepatitis suspicion (feeling sick, anorexia, vomiting, jaundice)
- Visit after 4 months V6: intervention + control arm
 - Clinical check, weight, temperature: signs and symptoms of TB absent?
 - Give treatment, record attendance
 - Sputum smear for AFB: Cat. 2 positive at month 3 only
 - Refer for rapid DST if AFB-positive; switch to MDR treatment if rifampicin resistant
 - Enquire, register adverse effects. Stop all drugs and refer in case of hepatitis suspicion (feeling sick, anorexia, vomiting, jaundice)
- Visit after 5 months V7: intervention + control arm
 - Clinical check, weight, temperature: signs and symptoms of TB absent?
 - Give treatment, record attendance
 - Sputum smear for AFB: all patients
 - Declare failure if positive and refer for rapid DST if AFB-positive
 - Switch to MDR treatment if rifampicin resistant

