5.4 Laboratory procedures

All analysis of clinical trial samples will be carried out in compliance with Good Clinical Laboratory Practice (GCLP). A Lab Analytical Plan will be available, in line with WHO-GCLP

FDA vital staining at 1 and 2 weeks will be used as part of the screening to identify intervention arm patients to be referred for rapid DST, and promptly switched to the MDR regimen if rifampicin resistant. Also an auramine AFB smear will be performed for comparison with FDA screening. Further follow-up will be standard and the same in the study and control cohort, by auramine AFB-smear at 2/3 months, 5 months and at end of treatment, when patients may again be referred for DST. Patients found positive on smear will be declared failure as per NTP definitions and registered for retreatment. Also relapse will be declared based on smears, as per NTP definitions. All failure and relapse cases will have sputum referred for conventional culture and DST, besides the rapid screening for rifampicin resistance. If not found resistant to this drug, such recurrence patients belonging to the intervention arm will not be re-started on the standard Cat. 2 but on the study regimen.

The initial, ethanol preserved pre-treatment specimen from all enrolled cases will be forwarded to ITM, Antwerp, for DNA sequencing of the *rpoB* gene. The *katG* and *inhA* genes will only be sequenced if an *rpoB* mutation is detected. All strains from cases diagnosed with rifampicin resistance at any time (2 weeks; failure; relapse or default), and all failure or relapse recurrence strains will also be forwarded to ITM, Antwerp. ITM will perform full DST and species identification, besides DNA sequencing of the *rpoB* genes. This will allow to compare the distribution of resistance-conferring mutations in the two study arms, and to identify possible acquired rifampicin resistance comparing

with the pre-treatment sequence. Spoligotyping on both pre-treatment sputum and recurrence isolate will be performed for confirmation of strain identity of all recurrences, to avoid confusion with re-infection, and to confirm presumed acquired resistance.

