8.3.4 Secondary and tertiary analysis

Secondary Objectives

1. *To assess whether the study regimen also cures low-level rifampicin resistant TB*

Adverse treatment outcomes will be described and compared among treatment groups in subgroups defined by initial rifampicin resistance mutations (performed in all patients) detected:

- none

- low-level
- high

2. *To assess the effectiveness of standard auramine versus FDA vital staining screening at two weeks of treatment for early switch of non-responding rifampicin resistant TB to MDR-TB treatment*

The proportion of initial rifampicin resistant case detected by FDA (i.e. the sensitivity of FDA) will be estimated together with 95% CI. The same analysis will be performed for auramine or ZN AFB smears and compared with FDA. Also the number of referrals needed with both techniques will be compared.

3. *To assess the negative predictive value of conversion at 2 weeks for relapse*

The Negative Predictive value (and 95% CI) of conversion in the intervention arm will be estimated as the % of relapses among those with a minimum 1 log decline in the number of AFB, or who are already negative or only scanty positive on AFB smear (auramine or FDA) at week 2.

4. *To estimate the proportion of acquired rifampicin resistance among failures and relapses*

Proportions will be estimated together with 95% confidence intervals, using the number of failure / relapse cases without mutation detected at diagnosis as the denominator and comparing intervention and control arms.

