#### 4.2. Efficacy study endpoints

##### *Primary endpoint*

The primary efficacy endpoint is the incidence of adverse treatment outcomes. Following the WHO guidelines from 2010, as currently in use in the NTP in Bangladesh, an adverse treatment outcome is defined as any occurrence of the following:

- Relapse: Cured previously from TB or completed treatment for TB and now having bacteriologically positive sputum for TB (at 12 months follow-up or at an earlier time point)
- Default: The patient whose treatment was interrupted for 2 consecutive months or more.

- Failure: Sputum positive for TB at 5 months or later during treatment. Failure will also be declared if the regimen has to be changed for at least 2 drugs due to adverse events.
- Death: All-cause mortality between case registration and end of TB treatment (related or not to TB or TB treatment)

Patients who are transferred out will be excluded from the outcome analysis.

In line with current WHO recommendations, patients detected with MDR-TB or rifampicin resistance before any outcome applies and switched to the MDR-TB regimen will be excluded from the outcome analysis.

Analyses will be performed using the NTP smear-based recurrence (failure, relapse) definitions, but as a secondary approach culture-based definitions will be used. In each analysis, if a patient has two events for the analysis of interest, the first endpoint will be taken into account, except for cured/completed followed by relapse which is considered as relapse.

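### Comparing arms on acquired rifampicin resistance as a share of failures and relapses leaves out cases switched before month 5 and dilutes a partial protective effect

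*SAP*

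**What the plan says.** Secondary objective 4 is to estimate the share of failures and relapses that have acquired rifampicin resistance. SAP 7.4 gives this per arm with Wilson intervals, "using the number of failure / relapse cases without mutation detected at diagnosis as the denominator". Protocol 8.3.4 uses the same fraction and adds a contrast: "using the number of failure / relapse cases without mutation detected at diagnosis as the denominator and comparing intervention and control arms".

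Three other provisions decide who can enter the fraction:

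- Bacteriological failure means "Sputum positive for TB at 5 months or later during treatment" (SAP 4.2). Relapse requires earlier cure or completion.
- Smear-positive patients can be tested and switched before that. At month 3, for example, Protocol 5.3 says "Refer for rapid DST if AFB-positive (auramine and FDA); switch to MDR treatment if rifampicin resistant".
- SAP 4.2 then states that "patients detected with MDR-TB or rifampicin resistance before any outcome applies and switched to the MDR-TB regimen will be excluded from the outcome analysis". Protocol 3.1 has the same rule. SAP 4.2 also ties the secondary objectives to these outcome definitions.

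Protocol 1.1 lists prevention of MDR-TB among the expected benefits. Protocol 2.1 names "possible favourable effects on initially present low-resistance mutations / mutations acquired during treatment" among the considerations for the follow-on trial.

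**The concern.** The expected benefit is that fewer treated patients acquire resistance. The planned fraction answers a different question: among patients who failed or relapsed, how many had acquired resistance.

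Resistance acquired on treatment and detected before month 5 contributes to neither the numerator nor the denominator. SAP 7.2 does not recover it, because that analysis counts initial resistance only.

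Among the cases that do count, the comparison conditions on an outcome that treatment affects. If high-dose rifampicin prevents susceptible relapses, the intervention arm's denominator shrinks and its proportion is pushed up. The randomised comparison is lost, and a real but partial reduction is understated.

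**Working it through.** The documents state no expected figure for this objective, so there is none to reproduce. The inputs come from Protocol 8.4 unless marked as assumed.

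**Control-arm counts**
- Failures plus relapses: 500 × (2% + 2%) = 20.
- Culture-positive: 20 × 50% = 10.
- Rifampicin-resistant: about half, so 5 resistant and s = 5 susceptible.
- The 5 resistant cases are not split into initial and acquired. The number acquired, a, can therefore be anything from 0 to 5. I take a = 2 (assumed) and vary it below.
- Planned ratio for susceptible relapse: Rs = 2/3.
- Initial resistance: about 10 per arm, leaving about 490 wild-type patients per arm.

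**What the planned fraction estimates**

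Control: a/(a + s). Intervention: Ra·a/(Ra·a + Rs·s), where Ra is the true ratio for acquired resistance. The observed ratio is Ra × (a + s)/(Ra·a + Rs·s). The last factor exceeds 1 whenever the total of such cases falls, so for 0 < Ra < 1 the ratio moves towards or past 1. The fraction is flat at Ra = Rs and reversed when Rs < Ra < 1.

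**True halving (Ra = 0.5, assumed), a = 2, s = 5**

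| Susceptible cases in the intervention arm | Control | Intervention | Observed ratio |
|---|---|---|---|
| 2/3 applied to all 5: 3.33 | 2/7 = 28.6% | 1/4.33 = 23.1% | 0.81 |
| 2/3 applied to relapses only, assumed half of the 5: 2.5 + 1.67 = 4.17 | 28.6% | 1/5.17 = 19.4% | 0.68 |
| Halved: 2.5 | 28.6% | 1/3.5 = 28.6% | 1.00 |
| Cut to one third: 1.67 | 28.6% | 1/2.67 = 37.5% | 1.31 |

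The true ratio is 0.50 in every row. Only the first two rows use the planned two-thirds. The last two need a larger fall in susceptible cases than the protocol expects.

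**Other values of a, Rs = 2/3 on all susceptible cases, Ra = 0.5**
- a = 1: 1/6 = 16.7% against 0.5/3.83 = 13.0%, ratio 0.78.
- a = 3: 3/8 = 37.5% against 1.5/4.83 = 31.0%, ratio 0.83.
- a = 5: 5/10 = 50.0% against 2.5/5.83 = 42.9%, ratio 0.86.

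**Other values of Ra, a = 2, Rs = 2/3**
- Ra = 0.8: 28.6% against 1.6/4.93 = 32.4%, so a 20% reduction reads as an increase.
- Ra = 0: 28.6% against 0%. There is no reversal. Protocol 8.4 expects resistant failure and relapse to be prevented.

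**Per wild-type patient randomised**
- Halving: 2/490 = 0.41% (Wilson 0.11 to 1.48) against 1/490 = 0.20% (0.04 to 1.15). The ratio is 0.50 and the difference is 1/490 = 0.20 percentage points.
- If two more control patients acquired resistance and were switched at months 2 to 4 (assumed), the planned fraction would stay at 2/7. The per-randomised figure would become 4/490 = 0.82% (0.32 to 2.08).

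**The case against.** The strongest defence is that SAP 7.4 delivers objective 4 as worded: per-arm proportions, with no test. Where the SAP means to compare arms, as in 7.2 and 7.6, it names a test. This stands for the SAP text. The comparison comes from Protocol 8.3.4, which the SAP does not withdraw, and two proportions side by side invite the same reading.

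A reader might infer that early acquired cases are lost to the trial. They are not. Protocol 5.4 sends to the reference laboratory "All strains from cases diagnosed with rifampicin resistance at any time (2 weeks; failure; relapse or default"), for comparison with the pre-treatment sequence. What is missing is an analysis that uses these results.

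The early route is also narrow. Month 2 referral additionally requires poor clinical evolution, month 3 smears on Cat. 1 are only for those positive at month 2, and month 4 smears are for Cat. 2 only. No document figure says how many such cases to expect.

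A reader might also infer that this fraction drives the go/no-go decision. Only Protocol 2.1 mentions acquired mutations there. Protocol section 8 and the SAP Introduction omit them, and that analysis excludes relapse, so it cannot be the SAP 7.4 figure.

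Finally, a count at any time has its own weakness. Week-2 testing is triggered by FDA decline in one arm and by fever in the other, so early detection is unequal. Minority resistance missed at baseline, or re-infection, could also be counted as acquired. This is a fair objection, and the fix has to deal with it.

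**Conclusion.** The concern holds for the between-arm comparison. The planned proportion omits resistance acquired and switched before month 5, and it conditions on an outcome that the regimen is meant to reduce. With the planned two-thirds ratio applied to all susceptible cases and a true halving, the observed ratio is 0.78 to 0.86 for 1 to 5 acquired control cases. It is 0.68 for 2 acquired cases if the ratio applies to relapses only and these are half of the susceptible cases. The halving, the acquired counts and that split are assumptions.

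The tempting stronger reading is that the measure will show no change, or harm, when acquired resistance has halved. The documents do not support it: that needs susceptible cases cut to half or less. Reversal is possible for a weaker effect (two thirds < Ra < 1), and it does not occur if resistant failure and relapse are fully prevented.

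Precision is poor either way: 2/7 has a Wilson interval of 8.2% to 64.1%. The correction changes what is estimated and does not make it precise. As a within-arm description of objective 4, SAP 7.4 can stand.

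**What to change.** In SAP 7.4:

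1. Keep the proportion among failures and relapses, labelled as a within-arm description.
2. For the between-arm comparison, add the number of patients with wild-type initial rpoB who later have rifampicin resistance confirmed by the reference laboratory, with the same strain by spoligotyping. Include those switched before month 5. Divide by all randomised patients with wild-type initial rpoB. Give Wilson intervals per arm and a risk difference with its interval.
3. Tabulate these cases by time of detection: week 2, months 2 to 4, month 5 or later during treatment, and relapse.
4. Add a sensitivity count without detections from the week-2 DST referral, because that trigger differs by arm.

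The cost is SAP wording and one table. Initial rpoB sequencing of all enrolled patients and referral of resistant strains found at any time are already planned. Protocol 5.4 plans spoligotyping for recurrences and to confirm presumed acquired resistance. If that is not taken to cover isolates from early-switched patients, those isolates would also have to be typed. The remaining drawbacks are very small counts, wide intervals and some residual dependence on arm-specific early testing.

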Xpert MTB/RIF testing will be performed as per manufacturer's instructions. A rifampicin resistant result will prompt to more extensive rapid DST using the slide technique.

A rifampicin resistant result by any test will be considered as correct and used to start MDR treatment promptly; only if there is serious doubt regarding correct patient identification the same test will be repeated on another sample for confirmation. However, for analysis the ITM result will override local results if different.

Sequencing of the *rpoB*, *katG* and *inhA* genes

DNA from the alcohol-preserved sputa or strains is extracted using the Boom method; amplification by PCR of the *rpoB* gene primarily will target all known resistance conferring sequences using extended primers, with a repeat PCR targeting only the shorter fragment of core region I in case the large-fragment PCR fails.²⁰ The genes conferring most resistance to isoniazid, i.e. *katG* and *inhA* will be sequenced only for sputa with an *rpoB* mutation already detected. DNA sequencing (ABI 3700 DNA capillary system) and comparison with the wildtype (H37Rv) sequence (ClustalX) will be performed for all amplified products.

The ITM SOPs followed are part of the study technical manual.

Fingerprinting techniques

DNA fingerprinting from sputum is best done by spoligotyping according to standard techniques, in view of the limited amount of material available.²¹ We have a large experience in comparing paired samples and isolates from the same patients, showing that spoligotyping is equally discriminating as 15-loci MIRU-VNTR for this application.

The ITM SOP followed is part of the study technical manual.

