8.4 Sample size and power

The sample size of two times 500 patients is a trade-off between precision and exposing an excessively high number of patients to potentially more toxic treatment. Power has not been taken into account, but if the results are favourable large scale cluster-randomized study will be designed to bring definitive proof.

The registered incidence of clinically apparent hepatitis from any cause during TB treatment is 1.5% for the study population. With the proposed sample size, an increase by at least 2% compared to the control arm will attain statistical significance ($p=0.047$).

With the standard (=control) regimens and definitions, about 2% failures and 2% relapses are currently notified by the DF project, but only 50% of those are culture-positive, and about half of the culture positive failures and relapses are rifampicin-resistant. Overall cure rate (new and retreatment cases together) is close to 90%, with 4% default and 4% deaths. Based on the data from 2010 about 20 cases with rifampicin resistance may be enrolled, 10 in each arm. We estimate that the more effective study regimen plus early detection of serious drug resistance rolled over to MDR-TB

treatment will prevent drug resistant failure and relapse, reduce rifampicin susceptible relapse to an estimated two third, and reduce death and default because of unrecognized rifampicin resistance to 80% of the control arm. This total estimated reduction of unfavourable outcome from 10% to 7% remains non-significant with the targeted enrolment of two times 500 cases. With 80% power and 95% confidence level, 2 x 1421 patients would have to be enrolled, which is not feasible and also difficult to justify. However, a slightly larger reduction of unfavourable outcome from 10% to 6.5% comparing two arms of 500 cases each would already result in a significant p-value. Additional evidence will be obtained studying *rpoB* mutations, initially (all smear-positives) and at time of failure or relapse (only in the few such cases expected). Absence of low-level resistance mutations only among patients with unfavourable outcome on the high-dose arm, while they were present among new cases in both arms, will be interpreted as additional evidence of effectiveness of the increased dosing.

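### SAP 7.4 estimates acquired rifampicin resistance over failure and relapse cases in which it may not be assessable; the denominator should require paired valid rpoB results.

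*SAP*

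**What the plan says.** SAP 7.4 asks for a proportion per arm with a Wilson interval, "using the number of failure / relapse cases without mutation detected at diagnosis as the denominator". Protocol 8.3.4 agrees ("Proportions will be estimated together with 95% confidence intervals, using the number of failure / relapse cases without mutation detected at diagnosis as the denominator") and adds a comparison of the arms. Cases with a mutation detected at baseline are thus already removed. Neither text sets a condition on the quality of the baseline sequence or on the existence of a recurrence result.

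Four other places determine who falls into that denominator:

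- **Outcome definition.** Under SAP 4.2 (and Protocol 3.1), "Failure will also be declared if the regimen has to be changed for at least 2 drugs due to adverse events". Failure and relapse are smear-based in the primary approach and culture-based in a secondary one.
- **Recurrence material.** Protocol 5.4 states that "all failure or relapse recurrence strains will also be forwarded to ITM, Antwerp". It identifies acquired resistance by comparison with the pre-treatment sequence and plans spoligotyping of the pair. The same section also allows molecular work on preserved sputum and gives every failure and relapse a rapid rifampicin test.
- **Baseline sequencing.** Protocol 5.4 foresees amplification failure, "with a repeat PCR targeting only the shorter fragment of core region I in case the large-fragment PCR fails".
- **Losses to follow-up.** Protocol 8.3.1 and 8.3.6 count them as failures in the intention-to-treat analysis. SAP 4.1.1 and 6.2b call them adverse treatment outcomes.

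**The concern.** A case can be classified as acquired or not acquired only if there is a usable sequence at baseline and a usable rifampicin result at recurrence. Followed as written, SAP 7.4 puts every other case in the not-acquired group by default.

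Three routes lead there:

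1. A patient declared a failure only for a two-drug change may have no positive sputum, and so nothing to sequence. If the protocol's label for losses to follow-up is used, those patients could enter in the same way.
2. A smear-positive recurrence without a valid rifampicin result adds to the denominator and can never reach the numerator.
3. Having no mutation detected covers both a confirmed wild type and a failed or short-fragment read. A mutation already present but not read at baseline would be labelled acquired if found at recurrence. Re-infection with a resistant strain would also be counted as acquired, because SAP 7.4 does not carry forward the spoligotype check.

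Routes 1 and 2 lower the proportion and route 3 can raise it. A single proportion with a Wilson interval shows neither. Protocol 2.1 names mutations acquired during treatment among the considerations for the next study, so the figure may be used beyond description.

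**Working it through.** **Plan figure.** The documents give no expected value or precision for this proportion, so there is none to reproduce. The sample size in Protocol 8.4 (1421 per arm for 10% versus 7%) recomputes to 1422 with a continuity correction, but this point does not depend on it.

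**Inputs**, all from Protocol 8.4 at control rates, with 500 patients per arm:

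- "about 2% failures and 2% relapses are currently notified by the DF project": 500 × (0.02 + 0.02) = 20 cases.
- "but only 50% of those are culture-positive": 20 × 0.5 = 10.
- "about half of the culture positive failures and relapses are rifampicin-resistant": 10 × 0.5 = 5.

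The protocol does not split the 5 resistant cases into initial and acquired. Let k be the number acquired (assumed), and suppose the other 5 − k were all detected at baseline and so removed.

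**Route 2, if only culture-positive cases can be typed.** SAP 7.4 gives k / (20 − (5 − k)) = k / (15 + k). Among typed cases it is k / (10 − (5 − k)) = k / (5 + k).

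| k | SAP 7.4 (Wilson 95%) | Typed cases only (Wilson 95%) | Ratio |
|---|---|---|---|
| 1 | 1/16 = 6.3% (1.1–28.3) | 1/6 = 16.7% (3.0–56.4) | 2.67 |
| 2 | 2/17 = 11.8% (3.3–34.3) | 2/7 = 28.6% (8.2–64.1) | 2.43 |
| 3 | 3/18 = 16.7% (5.8–39.2) | 3/8 = 37.5% (13.7–69.4) | 2.25 |
| 4 | 4/19 = 21.1% (8.5–43.3) | 4/9 = 44.4% (18.9–73.3) | 2.11 |

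The ratio of denominators is 20/10 = 2.0 if all 5 were acquired and 15/5 = 3.0 if none were.

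**Route 2, if preserved sputum also works.** Let e be the share of the 10 culture-negative cases that can be typed (assumed) and i = 5 − k. Dilution = (20 − i) / (10 − i + 10e).

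| e | i = 0 | i = 5 |
|---|---|---|
| 0 | 2.0 | 3.0 |
| 0.25 | 20/12.5 = 1.6 | 15/7.5 = 2.0 |
| 0.5 | 20/15 = 1.33 | 15/10 = 1.5 |
| 1 | 1.0 | 1.0 |

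**Route 1.** The documents give no frequency for two-drug changes. As an assumption, 5 such failures on top of the 20 would move 2/17 = 11.8% to 2/22 = 9.1% with no change in resistance. With culture-only typing, the dilution becomes 25/10 = 2.5 to 20/5 = 4.0.

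**Route 3.** No frequency is given for failed or short-fragment baseline reads. As an assumption, take k = 2 and let one of the 3 initially resistant cases be missed at baseline. It enters both numerator and denominator, and 2/17 = 11.8% becomes 3/18 = 16.7%.

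**Difference between arms.** No arm-specific rate of two-drug changes, of untyped recurrences or of failed baseline reads is given, so neither its size nor its sign can be derived.

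**The case against.** The strongest reply is that the laboratory plan already covers most of this.

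- **Typing without a culture.** Protocol 5.4 allows sequencing from ethanol-preserved sputum, refers to preservation of smear-positive recurrence sputa, and gives every failure and relapse rapid rifampicin testing. A culture-negative recurrence can therefore reach the numerator. This stands. A reader might infer from the culture figures that the proportion is diluted at least two-fold. The documents do not support that: two-fold is a scenario within a range of 1.0 to 3.0 for this route.
- **Culture-based definitions.** SAP 4.2 plans them as a secondary approach. This deals with much of the culture-negative part. Nothing says that it removes failures declared for adverse events, and it does not help with baseline reads.
- **Arm imbalance.** A reader might infer that high-dose rifampicin adds toxicity failures and so appears to suppress acquired resistance. The documents give no such rates. Protocol 7.1 expects that drugs can almost always be restarted without recurrence, and Protocol 1.1 calls the Cat. 2 regimen, used for control retreatment cases, the more toxic one. Even the direction is open. The assumed shift from 12% to 9% is also small beside an interval of 3% to 34%.
- **Decision weight.** Only Protocol 2.1 names acquired mutations. Protocol 8 and SAP 1 name effects on low-resistance mutations. The go/no-go analysis also excludes relapse, so the full proportion belongs mainly to the final analysis. This stands and lowers the stakes.
- **Target quantity.** The objective is worded as a proportion among failures and relapses, and conditioning on typability changes that. This is fair, and it is why the present proportion should stay as a secondary line.

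None of this removes the organism-free failures, or the merging of a wild-type baseline with no baseline result. The general imputation rule in SAP 6.2b does not address whether a sequence is evaluable.

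**Conclusion.** The concern holds in a limited form. The denominator excludes detected baseline mutations, so it would be wrong to say that it takes in all failures and relapses. It does admit cases in which acquired resistance cannot be assessed, and it counts them as not acquired. It also treats an unread baseline as mutation-free.

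Dilution from untyped recurrences is about two- to three-fold if typing needs a culture, and falls to 1.0 if every culture-negative recurrence is typed from sputum. This rests on the Protocol 8.4 programme rates applying to the trial and on all initial resistance being detected at baseline. Adverse-event failures would add to the dilution, while unread baselines and re-infection work the other way. The net direction is not known. Adverse-event failures could differ by arm, but no difference between arms is shown.

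This is a secondary, descriptive objective in a pilot study. The correction is still worth making because the rule as stated gives a proportion whose bias the reader cannot see.

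**What to change.** In SAP 7.4:

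- Make the main denominator bacteriological failures and relapses, leaving out failures declared only for an adverse-event regimen change. Require a valid wild-type baseline rpoB sequence and a valid recurrence rpoB result, from strain or preserved sputum, over the same region. Where the baseline was read only on the short fragment, compare only that fragment.
- Count resistance as acquired only if the paired spoligotypes match, using the typing already planned in Protocol 5.4.
- Report non-evaluable failures and relapses by arm and reason: no organism, no valid recurrence result, no valid baseline.
- Keep the present proportion as a secondary line.
- Reconcile the protocol and SAP labels for losses to follow-up, so that it is clear they do not enter this denominator as failures.

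This needs SAP wording and a derived flag, and no new samples. The price is a smaller denominator and a wider Wilson interval: in the culture-only scenario 6 to 9 cases per arm for k = 1 to 4, and for k = 2 an interval of 8% to 64% instead of 3% to 34%. If sputum typing succeeds in most cases, apart from any adverse-event failures the two lines will nearly coincide and little is lost.
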